In a prospective randomised trial the "ProTwin Trial"⁸ 813 women with twin pregnancies at a gestational age of 16 weeks to 20 weeks were randomised to either

pessary treatment or expectant management. Subgroup analysis of women with a shortened cervix below the 25 percentile (=38 mm) showed for the pessary group a significant 6-fold decrease in perinatal mortality and a reduction of severe morbidity. This demonstrates that an early screening followed by an early intervention is essential for patients at-risk. A secondary analysis “*per protocol*” of the ProTwinTrial revealed that the success of pessary treatment was mostly dependent on the correct placement and the duration of the therapy ⁹.

A further prospective-randomised trial by Goya et. al ¹⁰ also proved a significant reduction of the preterm delivery rate in twin pregnancies with cervical shortening (<25 mm, 20-24 weeks of gestation) after placement of a pessary compared to expectant management; the reduction in mortality was less pronounced than in the ProTwin Trial. A new case-control-trial by Fox et al. ¹¹ showed a decrease in early preterm birth before 32 weeks of gestation (4.8% vs. 28.6%, P=.05), a considerable prolongation of pregnancy (65.2 d. vs. 52.1 d, P=.025) and a reduced neonatal morbidity (9.5% vs. 34.9%, P=.04) in twin pregnancies after pessary therapy.

A secondary analysis of the ProTwin Trial indicated a higher survival rate without neurodevelopmental disability in the long-term outcome 3 years after pessary treatment (92.4 vs. 73.8%, p=0.006) compared to expectant management ¹².

A prospective, randomised controlled trial by Nikolaides ¹³ and a cohort study by Monfrance ¹⁴ in twin pregnancies with short cervix showed no significant effect of the pessary therapy compared to expectant management.

Up to now there is just one Cochrane review available concerning pessary therapy and the authors concluded that in spite of the positive effects seen that more trials should be conducted ¹⁵.

2.2. Description of the study population.

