A descriptive analysis by preterm birth will be carried out calculating means and medians for quantitative variables and proportions with 95% confidence intervals for categorical variables. In general, statistical comparisons with the pessary arm and the control arms or other group comparisons for primary and secondary outcomes will be performed with stratified tests as well as comparisons in the gestation subgroups. Events will be analysed for each twin and for single children assuming appropriate random effect regression models. Further subgroup analyses regarding the cervical length will be performed (e.g. CL 15 to 25mm and below 15mm). All tests, see also examples in the synopsis, will be two-sided using a significance level of $\alpha=0.05$.

For the primary endpoint we expect to have a drop out rate of up to 25% due to the long follow-up time (3 years) of the study; but we do not expect to have lost data for the secondary endpoints because for these parameters the study has a short follow-up time till time to birth only.

An interim analysis shall be conducted on key safety parameters after birth of 300 twins: the following safety endpoints will be assessed by a one-sided test with $\alpha=1\%$

- on level of the neonates: rate of preterm birth, time to birth, birth weight, death, neonatal morbidity, harm of intervention
- and on the maternal level: rate of hospitalisation for threatened preterm labour < 32 weeks, rate of PRoM <32 weeks, rate of infection / inflammation, rate of physical or psychological intolerance to pessary, rate of SAR/SAE, death.

The trial will be terminated as negative if a disadvantage for the pessary-treatment can be found in one of these tests. To guarantee a high safety level the significance level is chosen more conservatively than in a Bonferroni correction.

All analysis will be carried out with SPSS® version 19.0 or later (IBM Company SPSS Inc. Headquarters, Chicago, Illinois, USA) and R version 3.2.3 or later (R Foundation for Statistical Computing, Vienna, Austria).

Primary Outcome	Statistical Test
Children`s Long-Term Survival without Neuro-developmental Disability (3-Years-follow up)	Cochran-Mantel-Haenszel-Test, using 3 strata according to WoG
Secondary Outcome	Statistical Test
Birth before 34 Weeks of Gestation	Cochran-Mantel-Haenszel-Test, Chi-Quadrat Test
Time to Birth	Cox-Regression
Birthweight	van Elteren Test, Wilcoxon-Mann-Whitney Test
Fetal / Neonatal Death	Cochran-Mantel-Haenszel-Test, Chi-Quadrat Test

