Neonatal Morbidity	Cochran-Mantel-Haenszel-Test, Chi-Quadrat Test
Need for Hospitalization (mother)	Cochran-Mantel-Haenszel-Test, Chi-Quadrat Test
Days of Hospitalization (mother)	van Elteren Test, Wilcoxon-Mann-Whitney Test
Maternal Adverse Events	Cochran-Mantel-Haenszel-Test, Chi-Quadrat Test
Pessary Intolerance	Cochran-Mantel-Haenszel-Test, Chi-Quadrat Test
Vaginal Infections	Cochran-Mantel-Haenszel-Test, Chi-Quadrat Test

9.2. Expected number of subjects to be included.

For sample size calculation, we account for the stratified design and assume three equally large gestation groups. For the pessary group, we assume a combined event rate of at least 8% for the primary outcome and for the comparison of the pessary group with the control group we assume an odds ratio of 2.29. This odds ratio correspond to the lower bound of a one-sided confidence interval for the event rate given in van't Hooft (ProTwin Trial¹²). To reach a power of at least 80%, we have to evaluate at least 500 patients, 250 in the pessary group and 250 in the control group. To account for a drop out rate of 25%, overall n=672 pregnant women will be recruited.

9.3. Criteria for termination of the trial.

A non-justified case of maternal death (temporary stop until complete evaluation of the case by an external committee).

9.4. Selection of subjects to be included in each analysis.

The analysis will include all the subjects that have been randomised.

10. Direct Access to Data Source

Direct access will be granted to the authorized monitor, host institution and the regulatory authorities to permit trial-related monitoring, audits and inspections.

11. Quality and Control Assurance

Main investigator and collaborators: In order to ensure the Quality of the data they will provide instructions and training to the sites involved in the trial; review the CRF data; and detail of any other steps taken to ensure quality of research.

The main investigator will sign the study protocol and the “investigator’s commitment; he will apply for the Ethics Committee and the Director’s approval; and he will review the final report of the study.

The collaborators will assess patient’s eligibility, they will inform the patients and ask for the informed consent; and they will be responsible of the CRF and obtaining and registering all data.

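### Effects are to be tested separately within gestation and cervical-length subgroups, with no test of whether the effect differs between them

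*Combined protocol and SAP*

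**What the plan says.** Section 9.1 (Description of statistical methods) states that arm comparisons for primary and secondary outcomes "will be performed with stratified tests as well as comparisons in the gestation subgroups". It continues: "Further subgroup analyses regarding the cervical length will be performed (e.g. CL 15 to 25mm and below 15mm". The level is common to all of them: "All tests, see also examples in the synopsis, will be two-sided using a significance level of" 0.05.

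The table of tests at the end of 9.1 gives the stratified Cochran-Mantel-Haenszel (CMH) test for the primary outcome. Most binary secondary outcomes have the entry "Cochran-Mantel-Haenszel-Test, Chi-Quadrat Test". Birthweight and days of hospitalisation have the van Elteren and Wilcoxon-Mann-Whitney tests, and time to birth has Cox regression. No Breslow-Day or Woolf test and no treatment-by-subgroup term appears in the text or the table. Random-effect regression is mentioned only for events at twin or child level. No rule is given for interpreting subgroup results.

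Section 9.2 (Expected number of subjects) says of the sample size: "we account for the stratified design and assume three equally large gestation groups". It uses a single odds ratio of 2.29.

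Section 2.1 (Justification) comments on an earlier trial that randomised at 16 to 20 weeks: "This demonstrates that an early screening followed by an early intervention is essential for patients at-risk". Section 3 (Objective) sets no aim concerning differences in effect by gestation.

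**The concern.** Each within-subgroup test has the null hypothesis of no effect in that subgroup. Whether the effect is the same across subgroups is a different null hypothesis, and nothing in the plan tests it. The trial is built around three gestation windows, and its rationale stresses early intervention, so readers will set the three strata side by side.

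Each stratum holds about a third of the evaluable women and has far less than 80% power. Even if the pessary works equally well at every gestation, some strata will probably reach 5% and others will not. A report listing those verdicts invites the conclusion that the device works at some gestations and not at others. It also invites reading non-significance in a small stratum as absence of effect.

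**Working it through.** **Inputs.** From 9.2: pessary event rate 8%, odds ratio 2.29, three equal strata, 250 evaluable per arm, hence 250/3 ≈ 83 per arm per stratum. From 9.1: two-sided 5%. From 2.1: follow-up of an earlier trial with 92.4% versus 73.8% survival without disability. Assumed: uncorrected chi-square within each stratum, because the plan names no within-stratum test for the primary outcome.

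**1. The plan's own figure.** Control odds = 2.29 × 0.08/0.92 = 0.1991, so the control rate = 0.1991/1.1991 = 16.6%. The two-proportion formula with continuity correction gives 251 per arm (228 without), in line with the stated 250. Simulating the three-stratum CMH test gives power of 80.7% with continuity correction and 84.2% without. The assumptions below therefore match the design.

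**2. Power in one stratum.** Power = Φ[(d − 1.96·s0)/s1], with d = 0.166 − 0.080 = 0.0861, mean rate p̄ = 0.123 and n = 83:
- s0 = √(2·p̄(1 − p̄)/n) = 0.0510
- s1 = √((0.08·0.92 + 0.166·0.834)/n) = 0.0505
- (0.0861 − 0.0999)/0.0505 = −0.274, so power = 39.2%

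Exact binomial enumeration gives 39.4%.

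**3. Pattern over three strata when the effect is identical.** Call a result mixed if at least one stratum is significant and at least one is not. The strata are independent, so:
- all three significant: 0.392³ = 6.0%
- none significant: 0.608³ = 22.5%
- mixed: 1 − 0.060 − 0.225 = 71.5%

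Exact enumeration and simulation both give 71.7%. Among simulated trials with a significant overall CMH test, about 80% are mixed.

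**4. Sensitivity of the mixed-pattern figure (uniform effect throughout).**

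| Change | Mixed |
|---|---|
| Yates or Fisher within strata | 63-66% |
| Strata of 20/30/50% or 10/30/60% | 73-76% |
| All 672 women evaluable (112 per arm per stratum) | 75% |
| Pessary event rate 5-20%, odds ratio 2.29 | 60-74% |
| Odds ratio about 4.3 (7.6% vs 26.2% events, from 2.1) | 27% |
| Odds ratio about 4.3, pessary rate held at 8% | about 22-24% |
| Two equal cervical-length subgroups (assumed 125 per arm) | 2 × 0.545 × 0.455 = 50% |

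**5. A direct test of heterogeneity.** In the same simulation, a 2-df Woolf test on the log odds ratios (0.5 added to each cell) rejects in 3.2% of trials when the effect is uniform. Its power is low. With an 8% pessary rate and assumed true odds ratios of 4.3, 2.29 and 1.0 in the three strata, it rejects in about 38% of trials; with 2.29, 2.29 and 1.0, in about 14%.

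**The case against.** The strongest reply is that the plan promises no such inference. It proposes arm comparisons inside subgroups. It does not say that subgroups will be compared with each other, that effect modification will be claimed, or that a non-significant stratum means no benefit. The sentence in 2.1 on early intervention draws a lesson from an earlier trial and is not an aim of this one. This stands. A reader might take the 72% as a false-positive rate built into the plan, but it is the frequency of a pattern that can be misread. It is not the error rate of a planned decision, so it is not like for like with the 3.2% of a formal test.

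Three further limits also stand. The 72% belongs to the primary outcome, the gestation strata and an odds ratio of 2.29, which the plan took as a conservative lower bound. At the effect reported in the cited follow-up it falls to roughly a quarter. It does not carry over to cervical length, for which the documents give no subgroup sizes, and no figure was worked out for secondary outcomes.

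A reader might also infer that the primary analysis is invalid unless the odds ratio is common to all strata. That does not follow. The CMH test is valid under its null hypothesis without homogeneity; a common odds ratio matters for the pooled estimate and for power.

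The reply does not supply what is missing. Subgroup tests at 5% are planned, no test of a difference is planned, and no guidance on interpretation is given.

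**Conclusion.** The point holds as a gap in the supplementary analyses. The planned subgroup tests cannot support any statement that the effect differs by gestation or cervical length, and the plan contains nothing that could. Under its own primary-outcome assumptions, with uncorrected chi-square tests, a uniform benefit would give discordant verdicts across gestation strata in about 72% of trials. The figure depends mainly on the true effect size, less on the test used or the balance of the strata. The primary CMH test and the sample size are not affected. The change should be made before analysis, but the trial's main conclusion does not depend on it.

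**What to change.** In 9.1 and the table of tests:
- For the primary outcome, add one Breslow-Day test (or a treatment-by-gestation-group term in a logistic model) and one treatment-by-cervical-length interaction term. Keeping length continuous is preferable. The example bands stop at 25 mm, whereas section 2.2 sets the 25th centile at 32, 30 and 28 mm in the three windows, and the example wording leaves the cut-points open.
- Report subgroup odds ratios with 95% confidence intervals in place of separate 5% significance verdicts.
- Label all subgroup results exploratory, and allow a claim that the effect differs only on the interaction result.
- State that the interaction test has low power and that a non-significant result does not show homogeneity. Do not write that the overall estimate applies to every stratum when the test is non-significant; the 38% and 14% rejection rates above show how often that would extend a benefit to a stratum with none.

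The cost is a few lines of text and two added analyses on data already collected, with no change to sample size. The downside is that real differences between strata may go unconfirmed; the intervals will show that uncertainty.

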Women attending the reference hospital due to cervical shortening in twin pregnancies and fulfil the entry criteria (dichorionic twin pregnancy with cervical shortening \leq 25th percentile and do not fulfil the exclusion criteria), the study will be proposed. The patients will be informed of the intended therapeutic effect and possible side effects. If they agree and after obtaining their informed consent, they will be randomised according to the respective gestational week to either usual management (=control group) or cervical pessary placement up to 37 weeks (=pessary group). According to the gestational week and when the cervical shortening is under the 25th percentile the patients will be randomized to the following subgroups: gestational age in weeks 16-20, gestational age in weeks 20-24 and gestational age in weeks 24-28.

Specifically, the 25th centile of cervical length is defined at 32 mm, 30 mm and 28 mm for the 16+0 – 19+6, 20+0 – 23+6 and 24+0 – 28+0 weeks of gestation respectively.

2.3. Name and description of the device under investigation.

The Arabin cervical pessary, which is CE-certified for preventing SPB (CE 0482 / EN ISO 13485: 2012 + AC:2012 annex III of the council directive 93/42 EEC).

See annex I.

2.4. Statement that testing will be performed according to protocol, GCP and applicable legal requirements.

The Clinical Trial will be conducted following the protocol, the GCP, and all legal requirements.

3. Objective

This study aims to investigate the benefit of placing a cervical pessary in comparison to the expectant standard management in dichorionic twin pregnancies with cervical shortening \leq 25 percentile in terms of long-term survival without neurodevelopmental disability of the children.

Hereby, a standardized validated test called 'Ages and Stages 3rd edition' should evaluate the children's neurodevelopment at the age of 3 years. The test can be conducted by the parents and takes approximately 12 minutes. The questionnaires will be provided by the sponsor.

4. Design

4.1. Specific description of primary and secondary variables.

4.1.1. Primary outcome:

- Children`s survival without neurodevelopmental disability at the age of 3.

4.1.2. Secondary outcomes:

[figure not shown]
- Offspring
 - Time to birth
 - Preterm birth before 37 weeks: rate of delivery before 36+6 weeks
 - Preterm birth before 34 weeks: rate of delivery before 33+6 weeks
 - Preterm birth before 32 weeks: rate of delivery before 31+6 weeks

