A medically qualified investigator will assess the relationship of AEs to the study medication.

All SAEs must be reported to the main investigator. He will perform an initial check of the report, request any additional information, and he will notify it to the Ethics Committee. All SAE information will be recorded. It may be appropriate that some SAEs do not require immediate reporting but this must be justified. Justification might be determined, for example, by admission to hospital, or prolongation of hospitalization, where this is to be expected in the underlying disease or condition.

All adverse events (AE) life-threatening or resulting in death will be notified within 24 hours. All AE that are not life-threatening will be notified within 15 days. The rest of AE will be recorded and analyzed at the end of the study.

9. Statistics

9.1. Description of statistical methods.

The primary statistical aim is to compare the primary combined outcome “long-term survival without neuro-developmental disability at 3 years follow up” with a two-sided Cochran-Mantel-Haenszel-Test and a significance level of $\alpha=0.05$. The primary outcome refers to a combined event in any of the twin and will be analysed for all pregnancies with available primary endpoint. The stratified study design is accounted by this stratified test according to the gestation groups.

The main statistical evaluation will be performed at two time points. (1) The complete data set for the secondary endpoints will be available after the last women enrolled in this study has delivered her twins, so the analysis of these outcome parameter will be done right after this event. (2) The primary outcome will be evaluated 3 years after the last woman enrolled in this study has delivered her twins.

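### Subgroups are to be tested separately at 5% with no test of whether the effect differs between them, so gestation strata will often disagree on significance even if the pessary works equally in all three

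*Combined protocol and SAP*

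**What the plan says.** The primary outcome is to be compared "with a two-sided Cochran-Mantel-Haenszel-Test and a significance level of" 5%, stratified by the three gestation groups (section 9.1). For primary and secondary outcomes alike, section 9.1 then provides for "stratified tests as well as comparisons in the gestation subgroups". It continues: "Further subgroup analyses regarding the cervical length will be performed (e.g. CL 15 to 25mm and below 15mm". A general sentence says that all tests "will be two-sided using a significance level of" 5%.

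The sample size (section 9.2) rests on one common effect. The authors "assume three equally large gestation groups", and for the pessary group "we assume a combined event rate of at least 8% for the primary outcome"; for the comparison, "we assume an odds ratio of 2.29". No power is given for any subgroup.

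On eligibility, section 2.2 states that "the 25th centile of cervical length is defined at 32 mm, 30 mm and 28 mm" for the three gestation groups in order, from earliest to latest.

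No section names an interaction test, a test of homogeneity of odds ratios, a multiplicity rule for subgroups, or an exploratory status for them. The random-effects regression in section 9.1 is meant for events per twin and per child, and no interaction term is mentioned there.

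**The concern.** Whether the pessary works better at one gestation than another is a question about the difference between stratum effects. Separate p-values do not answer it. A significant result in one stratum and a non-significant one in the next can arise from the same odds ratio in both, and in small strata this is the usual result. The Cochran-Mantel-Haenszel test does not fill the gap, because it tests for a common association and not for differences between strata.

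The question matters here because gestation at placement defines the strata, and section 2.1 already argues from a cited subgroup result that early intervention is essential. Stratum p-values printed beside the main result invite a reading that the device works in one gestational window and not in another. The same comparisons are planned for the secondary outcomes. For cervical length, the bands are given only as examples, so the cut-points could be settled after the data are seen.

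**Working it through.** **Inputs (sections 9.1 and 9.2).** Two-sided 5% level; 250 evaluable women per arm; three equal strata, so 250/3 ≈ 83 per arm per stratum; event rate 8% in the pessary group; odds ratio 2.29.

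**Control rate.** Odds = (0.08/0.92) × 2.29 = 0.199, so the rate is 0.199/1.199 = 16.6%.

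**The plan's own sample size.** The usual two-proportion formula for 80% power is
n = [1.96·√(2p̄(1−p̄)) + 0.842·√(p₁(1−p₁) + p₂(1−p₂))]² / (p₂−p₁)².
With p̄ = 0.123 and p₂−p₁ = 0.0861, this gives 228 per arm, or 251 with continuity correction, against 250 stated. A simulated three-stratum Cochran-Mantel-Haenszel test at 83/83/84 per arm (200,000 runs) has 80.7% power with continuity correction and 84.2% without. The stated figure is reproduced, so these are the inputs the plan used.

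**Power in one stratum (83 per arm).** Φ{[0.0861·√83 − 1.96·√(2p̄(1−p̄))] / √(p₁(1−p₁) + p₂(1−p₂))} = Φ[(0.784 − 0.910)/0.461] = Φ(−0.274) = 39%. Exact enumeration of the chi-square test gives 39.4%, and 29.6% with continuity correction.

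**Chance that the strata disagree.** The strata contain different women and are independent. With power p in each, P(some but not all significant) = 1 − p³ − (1−p)³.

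| | p = 0.394 (uncorrected) | p = 0.296 (corrected) |
|---|---|---|
| All three significant, p³ | 6% | 3% |
| None significant, (1−p)³ | 22% | 35% |
| Some but not all | 72% | 63% |

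In the simulation, which uses uncorrected tests, the strata disagree in 72% of all trials and in 80% of those that succeed on the overall test. A homogeneity test of Woolf type is significant in about 3% of the same trials (nominal 5%).

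**How far this depends on the assumptions.**
- All 672 recruited women evaluable (112 per arm per stratum): 73 to 75%.
- Unequal strata, assumed splits 50/30/20 and 60/30/10: 73 and 76% (uncorrected).
- Two cervical-length groups covering everyone, smaller share assumed at 20 to 50%: exactly one is significant in 50 to 62% of trials (uncorrected).
- The larger effect cited in section 2.1 (92.4 versus 73.8%, odds ratio about 4.3): stratum power is about 90%, and disagreement falls to 1 − 0.90³ − 0.10³ ≈ 27%.
- No effect at all: at least one of three strata significant in 1 − 0.95³ = 14% of trials, for each outcome tested.

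**The case against.** The strongest reply is that the documents plan one confirmatory analysis, the stratified Cochran-Mantel-Haenszel test, and present the subgroup comparisons as additions to it. That stands. The type I error and power of the primary test are untouched. A reader might infer that the trial will probably report the pessary as effective at some gestations and not at others, but no section says that subgroup p-values will support a claim, or that strata will be contrasted by significance. The 63 to 72% is the chance of a mixed set of p-values, not of a wrong published conclusion.

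A reader might also take disagreement on significance to mean that the estimates will look different. The calculation does not show that. With a common odds ratio of 2.29, only about 10% of simulated trials have any stratum pointing the wrong way. The result also depends on effect size: section 9.2 describes 2.29 as a lower confidence bound, so it is a cautious value, and a larger true effect would bring more agreement.

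A third tempting reading is that women with a cervix above 25 mm are left out of the cervical-length analysis. The bands are introduced as examples, so a further group is not excluded. The fair criticism is that the bands are not fixed and that those named stop short of the eligibility limits.

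Finally, interaction tests have little power here. At 83 per arm per stratum, simulation with assumed stratum odds ratios gives the Woolf test 14% power for 2.29/2.29/1, 38% for 4.3/2.29/1 and 53% for 4.3/1/1. This is a real limitation of the remedy. It calls for caution about any subgroup claim; it does not make separate p-values the better evidence.

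**Conclusion.** The point holds as a weakness in the subgroup analysis, not in the primary inference. The plan prescribes within-subgroup testing at 5% and no test of the difference between subgroups. If the odds ratio is 2.29 in all three strata, with 83 evaluable women per arm in each, stratum power is 30 to 39% and the strata will disagree on significance in 63 to 72% of trials. The range reflects whether a continuity correction is used; the plan's 250 per arm matches the corrected calculation more closely. A homogeneity test would mislead in about 3%. The figures assume equal strata and the planned event rate, and they fall to about 27% at the larger effect cited in section 2.1. The change is worth making because it costs almost nothing and supplies the test that the subgroup question needs.

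**What to change.** In section 9.1:

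1. Add a test of treatment by gestation stratum, either Breslow-Day or an interaction term in a logistic model.
2. Add a test of treatment by cervical length, with length as a continuous term, in a model that also contains gestation stratum and its interaction with treatment. The eligibility limit for length differs by stratum (32, 30 and 28 mm), so length and gestation are linked; without these terms a gestation difference could appear as a length difference.
3. Report subgroup odds ratios with 95% confidence intervals, label any within-subgroup p-values exploratory, and state that a claim of differing effects rests on the interaction.
4. Replace the example bands with fixed ones covering all eligible women: below 15 mm, 15 to 25 mm, and above 25 mm up to the eligibility limit. The last band spans 32 − 25 = 7 mm in the earliest stratum and 28 − 25 = 3 mm in the latest, so the continuous analysis should carry the inference and the bands should serve for description.

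The cost is SAP wording and a few lines of code in R, which section 9.1 already names. No extra women or data are needed. The drawback is low power: moderate true differences may go unproven, and the plan should say that a non-significant interaction does not show equal effects.
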